9.2.3 Plain Radiography assessed Bone Tunnel Widening

BTW will additionally be assessed on plain radiograph. Bone tunnel width will be assessed at the widest part of the femoral bone tunnel. Bone tunnel width is defined as the largest distance between the opposing tunnel walls on a line orthogonal to the direction of the bone tunnel. Assessed will be the relative change in femoral bone tunnel width from baseline to respective follow-up.

9.2.4 Assessment of Other Outcomes of Interest

9.2.4.1 Clinical History

The following information regarding the clinical history of the patient will be gathered using eCRF:

- Date of the injury
- Affected side
- Activity at which injury occurred
- Mechanism of injury
- Comorbidities (if any)

9.2.4.2 Patient Demographics

The following information regarding patient demographics will be gathered using eCRF:

- Age
- Sex
- Height
- Weight
- Body Mass Index
- Smoking habit

9.2.4.3 Assessment during Surgery

The following information will be gathered at surgery:

- Date of surgery
- Comorbidities (if any) determined arthroscopically
- Additional surgical procedures (if any) not leading to patient exclusion (e.g. partial meniscectomy, meniscus repair)
- Side of autograft harvest (ipsilateral/contralateral)
- Tendon used (semitendinosus tendon with/without Gracilis tendon)
- Diameter of the femoral bone tunnel
- Diameter of the tibial bone tunnel
- Duration of the surgical procedure

9.2.5 Assessment of Safety Outcomes

9.2.5.1 Adverse Events

Intra-operative complications (if any) will be recorded on the eCRF. Self-reported AEs will be assessed by interviewing the patient. The following question will be used:

“Hatten Sie im Zusammenhang mit Ihrer Knieoperation irgendwelche nennenswerten medizinischen Probleme?”

Also any out of window visit or unexpected finding will be recorded. The following adverse event information will be recorded:

- Adverse event term
- Date of onset
- Date of resolution/Duration
- Severity (Subjective assessment by PI)
- Seriousness
- Relationship with surgical intervention
- Relationship with device under study
- Actions taken in response
- Outcome of the adverse event

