9.2.6 Assessments in Participants Who Prematurely Stop the Study

Study subjects who withdraw consent to participate or who fail to appear to the scheduled visits will be contacted by telephone in order to obtain the interview for self-reported AEs.

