10 SAFETY

10.1 Medical Device Category A studies

10.1.1 Definition and Assessment of safety related events

Adverse Event (AE)

Any untoward medical occurrence, unintended disease or injury or any untoward clinical signs (including an abnormal laboratory finding) in participants, users or other persons whether or not related to the investigational medical device [ISO 14155: 3.2].

Serious Adverse Event (SAE)

Adverse event that:

- results in death, or
- led to a serious deterioration in health that either:
 - results in a life-threatening illness or injury, or
 - results in a permanent impairment of a body structure or a body function, or
 - required in-patient or prolonged hospitalisation, or
 - results in medical or surgical intervention to prevent life threatening illness, or
- led to fetal distress, death or a congenital abnormality or birth defect. [ISO 14155: 3.37].

Health hazards that require measures

Findings that may require additional action are:

- Persistent anterior knee pain
- Septic arthritis
- Arthrofibrosis
- Graft rupture
- Aseptic effusion
- Subcutaneous cyst

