11.4.6 Safety Analysis

Safety will be evaluated by tabulations of AE's and SAE's and will be presented with descriptive statistics at baseline and follow-up visits for each treatment group. Inferential analyses of (serious) adverse events are not done.

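### The one scripted adverse-event question asks only for notable problems the patient links to the knee operation, so the AE and SAE tables will tend to run low against the protocol's own AE definition

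*Combined protocol and SAP*

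**What the plan says.** Section 9.2.5.1 sets the method for patient-reported events: "Self-reported AEs will be assessed by interviewing the patient. The following question will be used", followed by "Hatten Sie im Zusammenhang mit Ihrer Knieoperation irgendwelche nennenswerten medizinischen Probleme". In English, the patient is asked about any noteworthy medical problems in connection with the knee operation. No other AE question is scripted in the protocol.

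The same section then lists what is recorded for each event. The list includes severity as judged by the PI, seriousness, "Relationship with surgical intervention" and a separate field for relationship with the device.

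Patients who withdraw consent or do not attend "will be contacted by telephone in order to obtain the interview for self-reported AEs" (9.2.6).

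Section 10.1.1 defines an AE as "Any untoward medical occurrence, unintended disease or injury or any untoward clinical signs", "whether or not related to the investigational medical device". An SAE is an AE that meets one of several outcome criteria, in-patient hospitalisation among them. Section 11.4.6 provides for tabulations of AEs and SAEs, which "will be presented with descriptive statistics at baseline and follow-up visits for each treatment group".

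**The concern.** The question applies two filters that the definition does not contain. The patient must connect the problem with the operation, and must think it *nennenswert* (worth mentioning). A patient admitted to hospital for an illness she regards as unrelated to her knee can truthfully answer no, although the admission may meet the protocol's SAE definition.

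The form is built the other way round. Severity and relationship are fields completed once an event has been captured. With this wording, the patient makes a first judgement of both before the investigator sees anything.

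At stake is whether the AE and SAE tables mean what section 10.1.1 says they mean. This matters somewhat more here because the clinical investigations of the device described in section 3.3.1 were confined to oral, maxillofacial and cranial surgery. A systemic reaction is the kind of event that a patient might not attribute to a knee operation.

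**Working it through.** The plan states no expected AE rate, so there is no figure to reproduce. The check sets the sections side by side.

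**1. Scope of the definition against scope of the question**

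| Feature | Definition (10.1.1) | Scripted question (9.2.5.1) |
|---|---|---|
| Link to device | Not required | Not asked |
| Link to operation | Not required | Required, in the patient's judgement |
| Severity or importance | No threshold | Must be noteworthy to the patient |

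An event related to the operation but not to the device is still elicited. The gap consists of events the patient links to neither, plus events thought too minor to mention.

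**2. Scope of the output.** Section 11.4.6 tabulates AEs and SAEs by group and does not restrict them to related or operation-linked events. The SAE definition builds on the AE definition, so it carries no relationship condition either.

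**3. Other routes of capture**

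- 9.2.5.1: "Intra-operative complications (if any) will be recorded on the eCRF"; out-of-window visits and unexpected findings are also recorded.
- 9.3.3: the PI notes potential AEs at the follow-up examination. The study schedule has AE recording at all later visits.
- 6.3.2: a practitioner reviews the radiological images for safety.
- 8.7: the site tries to contact withdrawn patients for safety information.
- 12.1.2: records from other departments and hospitals count as source data.
- Section 15: the patient must report health-related complications to the PI, in the context of insurance cover.

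These routes either centre on the knee or depend on something coming to the site's notice. Section 8.7 gives no question of its own. None is a systematic enquiry about events the patient does not link to the operation.

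**4. Time for events to go unreported.** Scheduled contacts after surgery are at 42 days, 4.5 months, 1 year, 2 years and 5 years. Taking 42 days as 42/30.4375 ≈ 1.4 months, the gaps are about 1.4, 3.1, 7.5, 12 and 36 months.

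**5. Can the shortfall be sized?** Let *u* be the share of AEs the patient does not link to the operation, *m* the share of linked AEs not thought noteworthy, and *c* the share of the events so missed that other routes recover. Then

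share missed = 1 − [(1 − u)(1 − m) + c(u + (1 − u)m)].

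All three inputs are assumptions; the documents give none of them.

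- u = 0.2, m = 0, c = 0.5: 1 − [0.8 + 0.5 × 0.2] = 1 − 0.90 = 10%.
- u = 0.8, m = 0.2, c = 0: 1 − [0.2 × 0.8 + 0] = 1 − 0.16 = 84%.

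The shortfall is zero only if u and m are both zero, or if c = 1. The direction is therefore downward, but a range from 10% to 84% shows that the documents support no particular size.

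**The case against.** The strongest case on the other side has four parts.

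- **Capture does not rest on the question alone.** This is right. A reader might infer that an event the patient does not attribute to the operation can never reach the AE form. The documents do not support that: unexpected findings and out-of-window visits lead into the same form, and the examination, image review and outside records can each bring an event to light.
- **The device effects of most interest are the least likely to be lost.** This also stands. Section 3.6.2 anticipates subcutaneous and intratunnel cysts, and the hazards in section 10.1.1 include septic arthritis, arthrofibrosis, graft rupture and effusion. These arise in the knee, which is examined at every follow-up, radiographed at Visits 3 to 6 and scanned by CT at Visits 4 and 5. A reader might apply a general loss rate to device effects and compute a reduced chance of seeing one; nothing in the documents justifies that rate. Section 3.3.3 also reports an earlier randomised ACL trial of the device's bovine matrix, with no complications.
- **No comparison between arms is harmed.** A reader might infer bias between the groups. None is shown: the wording is the same in both arms, patients are blinded (6.3.2), and the safety analysis is descriptive.
- **The safety objective is narrower.** Section 4.4 speaks of intra- and postoperative complications, which an operation-linked question largely serves. But sections 10.1.1 and 11.4.6 do not narrow the AE and SAE tables in that way. If complications are all that is intended, the tables should say so.

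These points limit the consequence. They do not remove the mismatch, because no listed route asks about events outside the patient's own attribution.

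**Conclusion.** The concern holds in a limited form. Followed as written, the plan will tend to produce AE and SAE tables that are too low against its own definition, mainly for events outside the knee and for minor events. Some SAEs may be affected, such as an admission the patient regards as unrelated. The conclusion assumes that some patients will have events they do not link to the operation or do not think worth mentioning, and that the other routes will not recover all of them. The size is unknown. No bias between arms is shown, and the primary and secondary efficacy analyses are unaffected.

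**What to change.** In section 9.2.5.1, and so in the telephone interview of 9.2.6, replace the question with an open one that carries no attribution and no importance threshold. For example: *Hatten Sie seit dem letzten Kontakt irgendwelche gesundheitlichen Probleme?* (any health problems since the last contact). The investigator then judges severity, seriousness and relationship to surgery and device in the fields already on the form.

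If the sponsor prefers to keep the present question, section 11.4.6 should state that the tables cover operation-related events only, and the tables should be labelled accordingly.

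The first option costs one sentence in the protocol and on the eCRF. Its downside is that more minor, unrelated events will be recorded and assessed. Neither option changes an endpoint, the significance level or the sample size.

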CTCAE	Common terminology criteria for adverse events
eCRF	Electronic Case Report Form
FMEA	Failure Mode and Effects Analysis
H0	Null hypothesis
H1	Alternative hypothesis
HA	Hydroxyapatite
IFU	Instructions for use
IKDC	International Knee Documentation Committee
IKDC SKEF	IKDC Subjective Knee Evaluation Form
IMD	Investigational Medical Device
ISF	Investigator Site File
ITT	Intention to Treat
LHR	Law on human research
LKSS	Lysholm Knee Scoring Scale
MRI	Magnetic resonance imaging
PI	Principal Investigator
PLDLLA	Poly(l-lactide-co-D,L-lactide)
PLLA	poly-L-lactic acid
SAE	Serious Adverse Event
SDV	Source Data Verification
SN	Study Nurse
SNCTP	Swiss National Clinical Trial Portal
SOP	Standard Operating Procedure
TAS	Tegner Activity Scale
TMF	Trial Master File
WI	Work Instruction
β-TCP	β-Tricalcium phosphate

STUDY SCHEDULE

Study Periods	Screening	Surgery	Follow-up				
Visit	1	2	3	4	5	6*	7*
Time [days/weeks/months /years]	-3wk (±14d)	0	42d (±10d)	4.5m (±1m)	1 y (±2m)	2 y (±2m)	5 y (±4m)
Patient Information and Informed Consent	X*						
Demographics	X*						
Medical History	X						
In- /Exclusion Criteria	X*	X*					
Pregnancy Test		X*	X*	X*	X*	X*	
Clinical Examination		X	X	X	X	X*	X*
Randomization		X*					
CT scanning		X*		X*	X*		
Plain Radiography		X	X	X	X	X*	
Tegner Activity Scale		X	X	X	X	X*	X*
IKDC Subjective Knee Evaluation Form		X	X	X	X	X*	X*
Lysholm Knee Scoring Scale		X	X	X	X	X*	X*
KT-1000 Arthrometer Testing		X	X	X	X	X*	X*
Lachmann Test		X	X	X	X	X*	X*
Pivot Shift Test		X	X	X	X	X*	X*
Primary variables		X	X	X	X		
Secondary variables		X	X	X	X	X*	X*
Adverse Events		X*	X*	X*	X*	X*	X*

X* / * Study specific

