2.6 Declaration of Interest

This study will mainly be financed by ZuriMED Technologies AG.

PD [name] is co-inventor of a patent which is licensed to ZuriMED Technologies AG.

[name] is co-inventor of a patent which is licensed to ZuriMED Technologies AG. Also he is a shareholder of named company.

[name] is co-inventor of a patent which is licensed to ZuriMED Technologies AG. Also he is a shareholder and partially employed by named company.

[name] is partially employed by ZuriMED Technologies AG.

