4.4 Safety Objectives

Safety will be evaluated by the occurrence, frequency and severity of intra- and postoperative complications.

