6.3.2 Blinding Procedures

The current clinical trial is designed as a patient-blinded study.

Group allocation cannot be blinded to the operator nor can the group allocation be blinded to the practitioner evaluating the radiological images at regular postsurgical follow-up visit and for safety assessment.

Concealment of group allocation to the patient is ensured. During surgery, graft preparation and graft insertion is outside the patient's field of view.

No radiological images will be shown to the patient as to not reveal group allocation.

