9.3.3 Follow-up 1 (Visit 3)

Follow-up 1 will be performed 42 days after surgery. The patient will be asked to fill an online survey for all patient-completed questionnaires (IKDC SKEF, LKSS and TAS) in the clinic. Subsequently, the clinical examination is conducted by the PI recording the identical points as during the preoperative clinical examination and the occurrence of any potential AEs. Plain radiography measurement is performed according to ACLROCS_WI_PlainRadiography.

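### Adverse-event severity, a named part of the safety evaluation, is left to the PI's unanchored judgement, and the PI very probably knows the treatment arm

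*Combined protocol and SAP*

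**What the plan says.** Section 4.4, with the same sentence in the synopsis, states: "Safety will be evaluated by the occurrence, frequency and severity of intra- and postoperative complications". Section 9.2.5.1 lists what is recorded for each adverse event, and the severity entry is "Severity (Subjective assessment by PI". The same list has separate entries for seriousness, dates of onset and resolution, the action taken, the outcome, and the causal relation to the operation and to the device.

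Section 10.1.1 defines adverse and serious adverse events but sets no severity levels. The abbreviation list expands CTCAE as "Common terminology criteria for adverse events"; no section available for review uses it.

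On blinding, section 6.3.2 says "The current clinical trial is designed as a patient-blinded study". It adds that the operator cannot be kept unaware of the arm, and says of whoever reads the images: "nor can the group allocation be blinded to the practitioner evaluating the radiological images at regular postsurgical follow-up visit and for safety assessment". At follow-up 1 (section 9.3.3), "the clinical examination is conducted by the PI", who also records adverse events there; the later visits follow the same pattern. Section 11.4.6 plans descriptive tables of adverse and serious adverse events by treatment group, without inferential tests, and does not mention severity.

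**The concern.** A severity grade without definitions depends on whoever assigns it. If that person knows the arm, the same effusion or the same knee pain can be called mild in one arm and moderate in the other, and nothing in the plan fixes which call is correct.

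This matters most for events that need not meet the criteria for seriousness. Section 10.1.1 lists findings such as persistent anterior knee pain, aseptic effusion and subcutaneous cyst. When such an event is not serious, the PI's impression is its only severity grade. Section 3.3.1 says that clinical investigations of this device so far were confined to oral, maxillofacial and cranial surgery, so the adverse-event profile in ACL reconstruction is new information. At stake is the credibility of a between-arm description of severity, not the efficacy conclusion.

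**Working it through.** The plan gives no figure for this point, so the check is a reading across sections, followed by one line of arithmetic for scale.

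**1. Is severity a named safety component?** Yes, in the synopsis and section 4.4. Section 5.4, which lists the safety outcomes, does not repeat it.

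**2. Is a scale defined?** Section 9.2.5.1 assigns the grade to the PI's subjective view. Section 10.1.1 defines seriousness only. CTCAE occurs only as an abbreviation. Within the available text the answer is no; the eCRF itself cannot be seen.

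**3. Does the grader know the arm?** No sentence says so. The inference runs as follows:
- Section 6.3.2 limits blinding to the patient and says that a practitioner involved in follow-up imaging and safety assessment cannot be blinded.
- Section 9.3.3 has the PI carry out the follow-up examination and record adverse events.
- Section 9.2.5.1 puts relation to the device on the same record as severity. That judgement makes little sense without knowing whether the device was implanted.
- As further support, section 12.1.1 makes the PI responsible for the correctness of the recorded data. Under section 9.2.4.3 these include the femoral tunnel diameter, whose ranges in section 8.3 do not overlap between arms (9 to 9.5 mm against 8 to 8.5 mm).

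Together these make knowledge of the arm very probable.

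**4. What depends on the severity grade?** Whether an event occurred, how often, and whether it was serious are recorded separately. Self-reported events are elicited by a fixed question put to a patient who is blinded. The primary outcome is tunnel volume on CT, and the stopping rule in sections 11.3 and 11.4.5 uses the same kind of measurement at 4.5 months. None of these uses the severity grade.

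**5. Scale.** There are 56 patients in equal groups, so 56 / 2 = 28 per arm. Moving one patient from one severity category to another changes that arm's percentage by 1 / 28 = 3.6 points. With the 25 per arm left after the planned drop-out it is 1 / 25 = 4.0 points. This shows how sensitive a table of this size is. It does not estimate bias, because the documents state neither an expected event rate nor any severity levels.

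**The case against.** The strongest reply is that an anchored scale leaves the same unblinded PI doing the grading. This stands: definitions narrow the room for differential grading but do not close it. A grade built only from the treatment given would be weaker still. Its upper levels would largely repeat the seriousness criteria, it would say little about untreated symptoms, and treatment choices may themselves be made by people who know the arm. That is why a defined clinical scale is preferred to an action-based one.

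A second reply is that seriousness, action, duration and outcome are already recorded, so inconsistent severity calls could be found in a listing. This is partly right. It helps only if the listing is planned and there is a definition to check the calls against. How finely the action field is structured is not shown.

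Three stronger readings are tempting, and the documents do not support them:
- A reader might infer that a severity table will carry the safety conclusion. Section 11.4.6 promises tables of events and does not mention a severity table.
- A reader might infer that the grader has a financial interest. Section 2.6 records of more than one person that he or she "is co-inventor of a patent which is licensed to ZuriMED Technologies AG", but names are removed in the text available, so this cannot be tied to the person who grades severity.
- A reader might infer that the PI signs papers that reveal allocation. Section 9.3.2.1 has the PI sign the consent form and the pregnancy-test photograph, neither of which shows the arm. The allocation envelope is resealed, and nothing says that the PI signs it.

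**Conclusion.** The point holds as a modest design weakness. A component of safety named in section 4.4 is graded by stated subjective judgement, without an anchored scale in the available text, by someone who very probably knows the arm. Every severity entry in both arms is exposed to possible differential grading. Event counts, seriousness and the primary test are not affected through this route.

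The conclusion rests on two assumptions: that the PI's knowledge of the arm follows from sections 6.3.2, 9.2.5.1 and 9.3.3 read together, and that no scale is defined in the eCRF or in text not available for review. The direction and size of any bias are unknown. Correcting this is desirable rather than essential.

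**What to change.** In section 9.2.5.1, replace the PI's subjective assessment with a pre-specified anchored grade and written definitions for each level. CTCAE is the natural choice, since the protocol already lists it.

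In section 11.4.6, state that adverse events will be tabulated by that grade and by arm. State also that seriousness, duration, action taken and outcome will be listed beside each grade, so that the grading can be audited.

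The cost is one eCRF field, a sentence in each of the two sections, and slightly more coding work. Visits, treatment and sample size do not change. The limit should be stated in the report: the grader remains unblinded, so differential grading is reduced and made checkable, but not excluded.

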9.2.6 Assessments in Participants Who Prematurely Stop the Study

Study subjects who withdraw consent to participate or who fail to appear to the scheduled visits will be contacted by telephone in order to obtain the interview for self-reported AEs.

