Background and Rationale:	Reconstruction of the anterior cruciate ligament (ACL) using autograft tissue is currently recommended as the standard of care following an ACL tear or rupture, with the bone-tendon-bone (BTB) graft and hamstring tendon graft the most common. Although a BTB autograft is widely recognized to offer high mechanical performance and rapid graft healing, these advantages come at the cost of a longer surgery time and higher risk of severe patient discomfort at the graft harvest site. Use of a hamstring tendon autograft is less painful, but is generally slower to heal with higher risk of mechanical graft failure due to poor bone ingrowth. The aim of the current study is to augment graft-to-bone incorporation by use of an osteoconductive scaffold enlaced into the hamstring tendon autograft. This bovine derived composite bone substitute is inserted into the articular aperture of the femoral bone tunnel and should provide an osteoconductive / osteoinductive environment at a biomimetic attachment site leading to improved secondary graft-fixation and a reduced incidence of tunnel widening.
Objective(s):	
Primary objective of the study is to evaluate efficacy of the surgical technique for ACL reconstruction using an osteoconductive scaffold, enlaced into the hamstring tendon autograft, compared to the traditional technique.
 
Secondary objectives aim to assess the clinical outcome of the interventional treatment including patient subjective knee function and objective measures of knee stability.

Outcome(s):	
The primary efficacy outcome of this study will be the CT based relative change of the femoral bone tunnel volume.
 
Secondary outcome measures for patient subjective knee function include International Knee Documentation Committee Subjective Knee Evaluation Form, Lysholm Knee Scoring Scale and Tegner Activity Scale. Knee stability will be assessed using the KT-1000 Arthrometer Test, the Lachman Test and the Pivot Shift Test.
 
Safety will be evaluated by the occurrence, frequency and severity of intra- and postoperative complications.

Study design:	Randomized patient-blinded two-group parallel comparison trial using an active comparator.

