6.4 Unblinding Procedures

At patient study end - planned or unplanned - the patient will be informed about his/her group allocation in the trial.

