7.2 Recruitment and Screening

Patients who will undergo ACL-reconstruction at Balgrist University Hospital will be recruited for this trial. All patients will be informed about the purpose of the trial, the operation modalities, and their benefits as well as risks. Patients will be asked whether they are prepared to participate in the trial prior to their inclusion. The patients will be handed out the written patient information brochure and will be given a minimum of 7 days for consideration. Patients that gave written informed consent will be screened for the inclusion and exclusion criteria of the current trial. Patients who were screened but not enrolled in the trial (including patients unable to give informed consent due to any reason) will be documented in the screening log, recording the reason for exclusion.

All travel expenses for study-visits outside of standard of care will be reimbursed in the following way:

- Public transportation ticket from domicile to study site and back (2. Class, no Halbtax), or

- In case of travel by car: 0.50 CHF per kilometer from domicile to study site and back.

Study-visits outside of standard of care and therefore object of reimbursement are: Visit 6 and 7.

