8.7 Data Collection and Follow-up for Withdrawn Participants

For subjects who withdraw from the study prior to completion, the site will attempt to contact the subject in order to obtain safety information.

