9.2.2 Assessment of Secondary Outcomes

9.2.2.1 Assessment of Patient Subjective Knee Function

IKDC SKEF, LKSS and TAS are assessed with patient filled eCRFs using online surveys on a tablet computer. The procedure is conducted by the SN.

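### Missed visits prompt a call about adverse events only, so self-completed knee questionnaires go uncollected; separately, early stoppers may learn their allocation before their last adverse-event interview

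*Combined protocol and SAP*

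**What the plan says.** Section 9.2.6 sets one rule for two kinds of patient. "Study subjects who withdraw consent to participate or who fail to appear to the scheduled visits" are covered together, and they "will be contacted by telephone in order to obtain the interview for self-reported AEs". Section 8.7 is equally narrow for patients who withdraw: "the site will attempt to contact the subject in order to obtain safety information".

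The three questionnaires are secondary outcomes in the synopsis. Section 9.2.2.1 has them "assessed with patient filled eCRFs using online surveys on a tablet computer", with the study nurse running the procedure. Section 9.3.3 places completion in the clinic, and the later visits follow the same pattern. Nothing provides for completion elsewhere.

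On late follow-up, section 7.2 states: "Study-visits outside of standard of care and therefore object of reimbursement are: Visit 6 and 7". The study schedule gives these visits windows of ±2 months (2 years) and ±4 months (5 years). Section 11.5 uses no imputation.

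On unblinding, section 6.4 reads: "At patient study end - planned or unplanned - the patient will be informed about his/her group allocation in the trial". It sets no order relative to the contacts in 9.2.6 and 8.7.

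**The concern.** There are two gaps, and they affect largely different patients.

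**Missed visits.** A patient who does not attend but answers the telephone could still supply IKDC, Lysholm and Tegner scores. The examiner-performed tests (KT-1000, Lachman, pivot shift) cannot be obtained that way, but the questionnaires can. Visits 6 and 7 are the exposed ones: they fall outside routine care, neither has a CT, and Visit 7 has no radiograph, so questionnaires and the clinical examination carry most of the late comparison. If attendance depends on how the knee is doing, and does so differently by arm, a comparison of attenders is biased.

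**Early stoppers.** These are mainly patients who withdraw consent or are withdrawn under section 7.4. They reach an unplanned study end, which prompts both disclosure of the arm and a safety contact. If disclosure comes first, the patient answers an open question about medical problems after the knee operation (9.2.5.1) knowing the treatment received. The patient is the only party the protocol describes as blinded (6.3.2).

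**Working it through.** **The plan's own figures.** Section 11.2 uses a difference of 20% and an SD of 25.175%, with two-sided α = 0.05 and power 0.8. By the normal approximation, n = 2 × (1.96 + 0.84)² × (25.175/20)² ≈ 25 per group, and 50/0.9 = 55.6, rounded up to 56. Both stated figures reproduce. The 10% drop-out allowance was set for the CT endpoint; the documents give no attendance figure for 2 or 5 years.

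**Power for IKDC.** Section 11.2.1 gives a difference of 11.5 and an SD of 10, so the effect size is 1.15. A two-sided t-test with 25 per arm has power 0.978, against 0.98 stated. From 28 randomised per arm, an assumed 10% non-attendance leaves 28 × 0.9 ≈ 25, and 30% leaves 28 × 0.7 ≈ 20.

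| Completed forms per arm | IKDC power | Lysholm power |
|---|---|---|
| 28 | 0.988 | 0.999 |
| 25 | 0.978 | 0.999 |
| 20 | 0.943 | 0.993 |

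At the planned effect sizes, the loss of power is small.

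**Bias.** In each arm, let x be the fraction missing the visit and let the deficit be attender mean minus non-attender mean. The attender mean exceeds the full-arm mean by x × deficit. The bias in the between-arm difference is therefore

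x(intervention) × deficit(intervention) − x(control) × deficit(control).

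With the same x in both arms this is x × d, where d is the difference between the two deficits. Both x and d are assumed here.

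| x | d = 5 points | d = 15 points |
|---|---|---|
| 10% | 0.10 × 5 = 0.5 | 0.10 × 15 = 1.5 |
| 30% | 0.30 × 5 = 1.5 | 0.30 × 15 = 4.5 |

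Against the planned 11.5 points, that is 0.5/11.5 = 4% to 4.5/11.5 = 39%. If attendance and deficits are the same in both arms, d = 0 and the bias is zero. The sign depends on which arm has the larger deficit, which cannot be known in advance.

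**Order of disclosure and interview.** No arithmetic applies.
- Section 6.4 discloses allocation at an unplanned end.
- Section 7.4 brings about such an end for some patients, including those with graft re-rupture.
- Sections 8.7 and 9.2.6 then seek safety information.
- No section states which step comes first.
- Section 11.4.6 limits adverse events to descriptive tables, so no formal test is affected.

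**The case against.** Several points against the concern stand.

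- A missed appointment is not automatically a lost assessment. The windows allow a visit to be rebooked, out-of-window visits are recorded (9.2.5.1), and section 7.2 reimburses travel for exactly Visits 6 and 7. Section 11.5 also keeps the patient's other visits in the analysis.
- The upper end of the bias range needs a 15-point gap between the arms' deficits, for which the documents offer no source. It also equals the benefit of the fix only if every missed form is recovered.
- Remote completion is more than sending a link. The surveys run on a clinic tablet under the study nurse, and names are kept out of the eCRF (12.1.1), so a contact step is needed.
- Adverse-event severity is already judged by the principal investigator, and the tables are descriptive. Only the patient's own answer is exposed, in the few who stop early.

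A reader might also infer that the protocol has patients unblinded before the interview. It does not say so: it leaves the order open, and for a patient who simply fails to appear, the call may be the first chance to disclose anything. Nor is a single missed visit a study end, so the two gaps should not be read as one chain of events.

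What remains is that questionnaires are not requested from patients who are reached by telephone, and that nothing protects the order of interview and disclosure.

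**Conclusion.** Both gaps are real and modest. They concern secondary and safety outcomes; the CT primary outcome cannot be obtained by telephone and is untouched.

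For missed visits, the issue is possible selection bias. The 0.5 to 4.5 IKDC points rest wholly on the assumed 10 to 30% non-attendance and the assumed 5 to 15 point difference in deficit. The documents do not support treating the upper end as expected, or claiming that the secondary comparisons lose meaningful power.

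For early stoppers, the self-reported adverse-event answer may be unblinded. No size can be given: the documents state neither how many patients will stop early nor how far knowledge of the arm would change their answers.

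This is a cheap improvement in data collection rather than an error or contradiction in the plan.

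**What to change.** **Section 9.2.6.** For patients who miss a visit and have not withdrawn consent, use the planned call also to offer the existing online IKDC, Lysholm and Tegner surveys for that visit, and flag the responses as remote. Patients who have withdrawn consent stay outside this step. A separate question on re-rupture or revision is optional, since the adverse-event interview already asks about problems connected with the operation.

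**Section 6.4.** Disclose allocation only after the final adverse-event interview, and any final questionnaires the patient agrees to complete, have been obtained or attempted. Including attempts prevents an unreachable patient from blocking disclosure indefinitely.

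**Cost.** A short added procedure for the study nurse, including a way of sending the survey that respects the coded eCRF; a protocol amendment handled under section 2.10; and a possible difference between home and clinic responses, which the flag allows to be examined. The calls and the surveys themselves already exist.
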